- Permission to leave messages indicating research affiliation: Yes / No
- Age
- HIV status: Positive / Negative
- Cell phone: Yes / No
- Number of days in past 3 months when individual stopped using their cell phone

E. APPROACHING / ASSESSING PATIENTS

Before approaching the patient

Confirm with intake nurse via email that the RA will approach the new patient at their upcoming intake visit.

When heading to clinic, bring a clipboard with the:

- Screening form
- 2 copies of the consent form
- Release of Information form
- ClinCard FAQs and information documents
- Response cards set
- HIV education slides
- Mental health resources document
- Locator Form.
- Also bring a baseline questionnaire packet in case the patient immediately enrolls and wants to complete the baseline assessment while in clinic.

Remember, slides and consent show content related to the research study. Participants should be warned that these materials might reveal sensitive information. They can decline taking any of them.

Numbering system

Please use the following numbering system for identifying patients (PSID) and enrolling participants (SID): PSIDs=101-n; SIDs=1001-n

PSIDs should be assigned to every patient you identify and try to screen. That means that completed screens will not be continuously numbered – this is ok. The key is to assign a PSID to every new patient in the clinic.

Approaching the Patient

Patients are only approached and assessed during their free time during their clinical intake visit. Most staff are aware of this, but if the staff is not, please remind them that study staff are to only meet with patients during their free time.

Once you have met the patient, introduce yourself and ask if they have a few minutes to talk to you about an ongoing research study at the clinic. If they agree, administer the screener, which includes a brief recruitment script.

Patient consent

If a patient agrees to participate in the study, the staff will guide the patient through the consent form, answer any questions, and ask the patient to sign a copy of the consent form for our records.

After signing the consent form, the patient will need to complete the following:

- Engage Contact Locator Form

After completing these forms, the staff will set up a time to complete the baseline assessment with the patient later that day (if possible) or within 1 week.

Record all patient approaches in the “Key – HIV Engage” tracking file

F. PARTICIPANT PAYMENT (ClinCards)

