Multidimensional Scale of Perceived Social Support (MSPSS)	X	X	X	X	X	X
Berger HIV Stigma Scale	X	X	X	X	X	X
Healthcare System Distrust Scale	X	X	X	X	X	X

Everyday Discrimination Scale	X	X	X	X	X	X
Visit Specific Satisfaction Questionnaire	X	X				
Client Satisfaction Questionnaire-Revised	X	X				
End-of-Treatment Questionnaire	X	X				

I. REDCap ASSESSMENT DATABASE

This study uses a centralized REDCap database for all data collection and entry.

J. PROCEDURES FOR WITHDRAWAL OF CONSENT

If the participant communicates to research staff that they would like to withdraw their consent to be in the study at any point, the staff must document this in the Engage Tracking Log, and if possible, obtain written documentation from the participant via letter or in-person.

Once the participant has withdrawn consent, the staff no longer has permission to contact the participant regarding the study and will not review any electronic health record information about the individual.

K. PROCEDURE FOR WHEN PATIENT ENDORSES CURRENT SUICIDAL IDEATION/DISTRESS

The PHQ-9 should be administered early in the assessment so that a clinician can promptly respond. If a patient endorses current suicidal ideation at any time during any assessment, and/or as assessed by the PHQ-9 (i.e., score >0 on item #9) or otherwise in conversation, study staff will take the following steps:

- Immediately text a licensed study clinician to notify them that a risk assessment might be needed
- Administer the Modified Scale for Suicidal Ideation (MSSI) at the end of the assessment, unless the participant is in distress and interrupting the appointment is warranted
 - After collecting the MSSI information, explain to the individual that our study values our participants and wants to offer resources or help if needed.

- Ask who knows about the patient's suicidality (e.g., therapist, case manager). If there are providers who are aware of these issues, ask when the patient will speak to them next.
- Pause the assessment and call the study clinician (outside of the appointment room if conducting the assessment in-person). The clinician will then determine next steps based on the information gathered by the study staff.

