Brief Acceptance-Based Retention Intervention for Newly Diagnosed HIV Patients

NCT04201288

Statistical Analysis Plan – 4/23/19

Data analytic plan (Aim 1).

We will use logistic regression to test the hypothesis that compared with ETAU, ABBT will increase the likelihood of meeting minimum DHHS recommended HIV care. To test the hypothesis that ABBT will result in improved virologic suppression, relative to ETAU, MANCOVA will be used. Planned baseline covariates include age, gender, race-ethnicity, HIV viral load, and study site. Any baseline variables associated significantly ($p < .10$) with subject attrition will also be included as covariates. We will also co-vary for cumulative TAU exposure. A 2-tailed probability of Type I error $< .05$ will be used for all null hypothesis tests.

We will use latent growth models (LGM) to estimate the effect of intervention on ART adherence, disclosure of HIV status, perceived social support, and HIV stigmatization. Data will be available from baseline, 1-, 3-, 6-, 9-, and 12-month follow-ups. This approach offers the flexibility to accommodate outcomes with a range of exponential family (e.g., normal, binomial, etc.) error distributions and allows a comparison of possible alternative growth processes (linear, quadratic, unconstrained with freely estimated time values) describing change over time. Initially, the Satorra-Bentler Scaled Chi-Square⁸⁵ will be used to compare linear change, quadratic change, and models with freely estimated time values. After identifying the best fitting unconditional LGM, conditional LGM models will be estimated in which the intercept and slope growth factors will be regressed on group, age, gender, race/ethnicity, and any baseline measures that significantly ($p < .10$) predict attrition. Significant differences in slope growth factors are consistent with the hypothesis that the ABBT and ETAU arms experience different patterns of change over time.

Data analytic plan (Aim 2).

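### The Aim 1 growth models adjust for attrition through baseline measures alone; adding HIV care attendance as an auxiliary variable would cheaply guard against a possible bias in the arm difference

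*SAP*

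**What the plan says.** The second paragraph of the SAP's Aim 1 plan uses latent growth models "to estimate the effect of intervention on ART adherence, disclosure of HIV status, perceived social support, and HIV stigmatization". On timing it says "Data will be available from baseline, 1-, 3-, 6-, 9-, and 12-month follow-ups". After the shape of change is chosen, the intercept and slope factors "will be regressed on group, age, gender, race/ethnicity, and any baseline measures that significantly" predict attrition at p < .10. That is the only attrition provision for these models. The SAP names no missing-data estimator, imputation, weighting, auxiliary variable or sensitivity analysis.

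The first paragraph of the same plan, for the logistic and MANCOVA analyses, has a parallel baseline rule ("Any baseline variables associated significantly") and adds one post-baseline variable: "We will also co-vary for cumulative TAU exposure". That variable is not listed for the growth models. The first hypothesis is that "ABBT will increase the likelihood of meeting minimum DHHS recommended HIV care". The SAP's Aim 2 plan calls the growth-model outcomes secondary and extends the same models to mediation, where the care outcome appears as a distal outcome.

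Three places in the Protocol bear on what data exist:
- Section H allows follow-up assessments to be done remotely.
- Section J says that after withdrawal of consent staff "will not review any electronic health record information about the individual", which implies that records are reviewed otherwise.
- Section E lists a "Release of Information form" among the materials brought to the approach visit, without describing its use.

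Neither document states the data source of the care outcome.

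**The concern.** The intervention aims to keep people in care. If it works, fewer ABBT than ETAU participants leave care, and they leave after randomisation. A baseline covariate cannot represent an event that has not yet happened. Suppose leavers are harder to interview and also fare worse. Then more poor outcomes go unseen in ETAU than in ABBT, and a model without care status treats the unseen leavers like similar participants who stayed. The ETAU trajectory looks too good and the arm difference shrinks. Aim 2 extends the same models, so it would inherit the problem. Attendance is the natural variable to carry this information, and the record review implied by Protocol section J may supply it even when an interview is missed.

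**Working it through.** The documents give no sample size, retention, interview completion or effect size, so there is no figure of the plan's to reproduce. Every number below rests on assumed inputs.

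**Step 1: the mechanism by hand.** Let p be the proportion leaving care, c the month-12 interview completion among leavers, s the completion among stayers, d the leavers' deficit in SD, and e the rest of the ABBT effect. Assume p = 0.40 (ETAU) and 0.25 (ABBT), s = 0.92, c = 0.25 or 0.45, d = 0.5 or 0.8, e = 0.2.

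- True difference = e + d(0.40 − 0.25): 0.2 + 0.5 × 0.15 = 0.275, and 0.2 + 0.8 × 0.15 = 0.320.
- Share of leavers among those interviewed = pc / [pc + (1 − p)s]. At c = 0.25: ETAU 0.100/0.652 = 0.153, ABBT 0.0625/0.7525 = 0.083, gap 0.070. At c = 0.45: ETAU 0.180/0.732 = 0.246, ABBT 0.1125/0.8025 = 0.140, gap 0.106.
- Difference among those interviewed = e + d × gap. For d = 0.5: 0.235 (c = 0.25) and 0.253 (c = 0.45). For d = 0.8: 0.256 and 0.285.

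Using month-12 interviews alone, the estimate is therefore 8-20% too small. If p, c and s are equal in the two arms, both gaps are zero and the bias disappears.

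**Step 2: credit for earlier waves.** A likelihood fit also uses each person's earlier interviews. A simulation with the same inputs (maximum likelihood for a multivariate normal by arm, six waves, 20,000 per arm, 6 replicates) gave:

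| True difference | Without attendance | Shortfall | With one attendance indicator |
|---|---|---|---|
| 0.275 | 0.246-0.258 | 6-11% | 0.275-0.277 |
| 0.320 | 0.276-0.292 | 9-14% | 0.313-0.323 |

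Earlier waves recover part of the loss, and attendance recovers nearly all of the rest.

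**Step 3: the slope, and when bias arises.** A second simulation used a linear growth model fitted by full-information maximum likelihood, 100,000 per arm. Assumptions: random intercept SD 0.7, slope SD 0.5 per year, residual SD 0.6, direct slope difference 0.30 per year, and 30%, 60% or 90% of leavers losing all later interviews. Bias in the slope difference, against the estimate with no lost interviews:

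| Mechanism | Leaving, ETAU v ABBT | Bias |
|---|---|---|
| Unrelated to outcome | unequal or equal | at most 0.003 in size |
| Driven by earlier interview values | unequal or equal | at most 0.002 in size |
| Any mechanism tested, same in both arms | 30% v 30% | at most 0.003 in size |
| Tied to the person's underlying slope | 30% v 20% | −0.006 to −0.029 (2-10%) |
| Outcome drops 0.3 to 0.8 after leaving | 30% v 20% | −0.007 to −0.071 (2-19%) |
| Outcome drops 0.3 to 0.8 after leaving | 40% v 20% | −0.011 to −0.139 (3-29%) |

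The largest values need 90% of leavers' interviews to be lost. At 30% v 20% with 30% or 60% lost, the range for an outcome drop is 0.007/0.334 = 2% to 0.041/0.388 = 11%.

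Imputing lost waves within arm and time of leaving, from leavers still interviewed, cut the bias to 0.012 or less in size wherever there had been bias. For example, at 40% v 20% with a drop of 0.5 and 90% lost, the complete-data value was 0.411, the fit without care status 0.321 and the corrected value 0.412.

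**Step 4: realistic visit data.** With retention gaps of 10 to 15 points and completion among leavers of 25-60%, a further simulation gave shortfalls of about 2-16% on both the month-12 and slope scales. Noisy visit indicators for each interval removed most of this. With equal leaving in both arms the bias was negligible.

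**The case against.** The case against has real force.

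- **Bias is conditional.** It needs leaving care to predict unseen outcomes beyond earlier interviews, and to differ by arm. Several plausible mechanisms in step 3 give essentially none. This stands.
- **Baseline measures need not be the only protection.** If all available waves are fitted by likelihood, earlier interviews contribute too. This stands as a possibility, but the SAP does not commit to such a fit. The simulations already give the plan this credit.
- **Interviews need not stop when care stops.** Remote assessment, a locator form and $25 per assessment all support follow-up outside the clinic. This weakens the assumed link without removing it. It also helps the fix, which relies on some leavers still being interviewed.
- **The record data are inferred.** A reader might infer that attendance is already abstracted and known for everyone. The documents do not say so, and section J rules it out after withdrawal of consent.
- **The size is modest.** The shifts in step 2 run from 0.275 − 0.258 = 0.017 to 0.320 − 0.276 = 0.044 SD. The standard error of a two-arm mean difference in SD units is √(2/n): 0.20 at an assumed 50 per arm and 0.10 at 200, before missing data. The shift is thus about 0.1 to 0.4 standard errors, toward the null, on secondary outcomes. This supports treating the point as an improvement.
- **Attendance by interval is a noisy marker of leaving.** A visit may simply not be due in a short interval. Step 4 suggests that such markers still remove most of the bias.

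**Conclusion.** The point holds as a cheap improvement to a stated rule. The growth models adjust for attrition through baseline measures only and use no post-baseline care status, in a trial whose first hypothesis implies that care will differ by arm. Under assumed retention gaps of 10 to 15 points and completion among leavers of 25-60%, the arm difference can be roughly 2-16% too small. More extreme assumptions enlarge this, and equal leaving makes it about zero.

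A reader might infer that the planned estimates are biased, or that interviews end when care ends. The documents support neither: they give no retention or completion figures and allow remote follow-up. Confidence is medium, because the direction recurs across simulations while the inputs and the record source are assumptions.

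**What to change.** State that the growth models are fitted by full-information maximum likelihood on all randomised participants with at least one wave, and keep the baseline covariates. Add HIV care attendance in each interval between assessments as an auxiliary variable: through saturated correlates for continuous outcomes, and through multiple imputation by arm for binomial ones. Do not enter it as a covariate. It is measured after randomisation and may lie on the treatment pathway, so conditioning on it would stop the arm effect from being a total effect.

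State where attendance comes from; the record review implied by Protocol section J is the natural source. Add a missing-not-at-random sensitivity analysis, for example a delta shift, for participants whose later interviews or records are all missing. If every leaver's later interviews are lost, the auxiliary variable cannot recover a change that follows leaving.

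The cost is somewhat more model complexity and an imputation step for binomial outcomes. If attendance is already abstracted for the care outcome, no new data collection is needed. The change does not help after consent is withdrawn, when record review stops.

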The hypothesis that the effects of ABBT will be mediated by increased HIV acceptance and increased willingness to disclose HIV status will be tested in a latent growth model framework⁹¹. We will extend the LGMs estimated when testing the effects of ABBT on secondary outcomes (AIM 1). The slope growth factors in the LGM are latent variables that represent change trajectories which can be used to account for differences in more distal outcomes. For example, the likelihood of meeting minimum DHHS recommended HIV care.

Mediation is tested by specifying an indirect effect defined as the product of the effect of intervention on the slope growth factor of the hypothesized mediator (HIV acceptance, increased willingness to disclose) by the effect of the mediator on meeting DHHS recommended HIV care. Bias-corrected bootstrap resampling is generally recommended for testing the statistical significance of indirect effects⁹². Simulation studies have generally shown this method to be the most efficient method for testing mediational hypotheses^{64, 93}. Mplus⁸² statistical software has facilities to specify and estimate the LGM mediation models.

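### Aim 2 names no covariates for the non-randomised path from mediator to care, and neither Aim 1 list names the baseline depression and substance use scores that could confound it

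*SAP*

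**What the plan says.** The mediation test is in the SAP, Data analytic plan (Aim 2): "Mediation is tested by specifying an indirect effect defined as the product of the effect of intervention on the slope growth factor" of the proposed mediator, multiplied "by the effect of the mediator on meeting DHHS recommended HIV care". It is tested with a bias-corrected bootstrap. No covariate is named for the second factor.

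Two covariate lists exist, both under Aim 1.

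- **Logistic regression for care, and MANCOVA:** "Planned baseline covariates include age, gender, race-ethnicity, HIV viral load, and study site". Baseline variables associated at p < .10 "with subject attrition will also be included as covariates". The SAP then adds: "We will also co-vary for cumulative TAU exposure".
- **Latent growth models:** "the intercept and slope growth factors will be regressed on group, age, gender, race/ethnicity, and any baseline measures" that predict attrition at p < .10.

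Aim 2 is linked to the second list: "We will extend the LGMs estimated when testing the effects of ABBT on secondary outcomes (AIM 1". No sentence links it to the first.

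The posted protocol document (the Manual of Procedures), section H, Randomization, says that allocation uses each participant's baseline depression and substance use scores. Neither SAP list names them.

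**The concern.** Arm is randomised, so the arm effect on the mediator slope can be read causally. The mediator is not randomised. People whose acceptance or willingness to disclose rises faster may differ at baseline in ways that also keep them in care. Depression and substance use are obvious candidates, and the trial already treats both as important enough to guide allocation.

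If such a shared cause is left out of the care equation, its effect is credited to the mediator. Multiplied by a real arm effect on the mediator, this produces an apparent indirect effect. With opposite signs, the same mechanism shrinks or hides true mediation. What is at stake is the trial's statement about mechanism. The Aim 1 tests compare randomised arms and are not affected.

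**Working it through.** The documents give no sample size, power or effect size for either aim, so there is no planned figure to reproduce. The check has three parts.

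**1. Where the covariates sit.** The growth-model covariates are regressors of the intercept and slope factors. Extending those models brings the covariates to the mediator side and leaves the care equation unspecified. The scores enter only through the attrition rule, which tests a link with dropout and not with the mediator or care. Under the growth-model rule they would then sit on the growth factors. In simulation at N 150 and 300 with 10% to 30% attrition (all assumed), one score passes the p < .10 screen in about 10% of trials if unrelated to attrition, 20% to 55% at an odds ratio of 1.25 per SD, and 42% to 93% at 1.5.

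**2. Size of the bias.** Let the true mediator effect on care be zero. With the shared cause left out of the care equation, the mediator coefficient b is approximately

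b ≈ Cov(slope, log-odds of care | arm) / Var(slope | arm).

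- One standardised cause moving the slope by 0.3 SD and care by 0.5 log-odds, with slope variance 1 within arm: 0.3 × 0.5 / 1 = 0.15. Simulated mean: about 0.15.
- A stronger cause, 0.4 SD and 0.8: 0.4 × 0.8 = 0.32. Simulated: about 0.31.

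The false indirect effect is (arm effect) × b. With an arm effect of 0.5 and b = 0.15 it is 0.075. With an arm effect of zero it is zero, so a real arm effect on the mediator is needed.

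For two scores correlated 0.3, each with effect s, the combined effect is √(2 × s² × 1.3):

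- s = 0.3: √0.234 = 0.48
- s = 0.2: √0.104 = 0.32
- s = 0.1: √0.026 = 0.16

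With residual slope variance 1 and before dilution by measurement noise, b is about 0.234/1.234 = 0.19, 0.104/1.104 = 0.09 and 0.026/1.026 = 0.03.

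**3. How often mediation is falsely declared.** The inputs are all assumed: total N 150 or 300, arm effect 0.3 or 0.5 SD on the slope, care about 65% against 79%, and waves at 0, 1, 3, 6, 9 and 12 months. Per-person slopes stand in for the latent slope. Arm is in the care model, the interval is bias-corrected, and there are 1000 trials per cell (simulation error up to about 1.5 points). Percentages at s = 0.3, with the no-confounding rate for reference:

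| Arm effect, N | No confounding, as written | As written | Aim 1 care list carried over | Scores on slope only | Scores on both paths |
|---|---|---|---|---|---|
| 0.3, 150 | 2.7 | 6.4 | 5.9 | 6.2 | 2.5 |
| 0.3, 300 | 4.6 | 19.9 | 19.1 | 22.0 | 3.8 |
| 0.5, 150 | 4.7 | 13.3 | 12.6 | 14.9 | 4.8 |
| 0.5, 300 | 7.4 | 30.6 | 29.5 | 31.5 | 8.6 |

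Over the same four cells, as written against adjusted:

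- s = 0.2: 3.2 vs 3.0, 8.4 vs 4.9, 7.4 vs 4.9, 14.1 vs 7.6
- s = 0.1: 2.7 vs 2.5, 4.2 vs 3.9, 5.8 vs 5.2, 7.6 vs 7.5

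The last column of the table came from a wider adjustment that also covered the mediator's starting level and simulated Aim 1 covariates. A separate run with only the two scores on both paths (arm 0.5, s = 0.3) gave 12.5% falling to 3.5% at N 150 and 31.8% falling to 8.8% at N 300. With scores measured at reliability 0.8, the wider adjustment still took 13.5% to 4.9% and 30.0% to 7.6%.

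A different set-up, with one confounder (0.3 SD, 0.5 log-odds) and an arm effect of 0.5, gave 11.2% at N 100 and 26.0% at N 200. These were 10.8% and 24.4% with the confounder on the mediator only, and 4.4% and 9.2% with it on both paths. With no arm effect on the mediator and the stronger confounder, the two unadjusted or mediator-only analyses stayed at 2.4% to 8.8%.

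**The case against.** The strongest reply is that the SAP is brief rather than wrong. Aim 2 extends models that have covariates, and Aim 1 already lists covariates for the same care outcome, so a reasonable analyst would use them. That stands as far as it goes: the text shows under-specification, not a decision to leave covariates out. But the charitable reading does not solve the problem. The Aim 1 care list does not name either score, and carrying it over leaves 5.9% to 29.5% in the table.

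Several limits on size also stand. Nothing in the documents shows that depression or substance use drives acceptance, disclosure or care; their use in allocation concerns balance between arms. An effect of 0.3 per score is about 0.48 combined, or 0.234/1.234 = 19% of slope variance. The 30.6% is the corner with the largest N, arm effect and confounding. The bias-corrected interval itself rejects in up to 7.4% of trials without confounding, so each cell should be compared with its own reference. And if the scores predict attrition strongly, the screen will often admit them.

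Using the scores at randomisation is no answer to the concern. It balances the arms but leaves the within-arm link between scores, mediator change and care.

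The objection that adjustment is expensive is right for a long list and not for two scores; see the cost under the fix.

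**Conclusion.** The point holds as a change that should be made. The path from mediator to care has no stated covariates, and neither Aim 1 list names two baseline scores that are already collected and used for allocation. If those scores affect both mediator change and care, and the arm moves the mediator, the false-mediation rate under the assumed inputs is about 6% to 31% as written and about 3% to 9% with the scores on both paths, at 0.3 per score. At 0.1 per score there is no real difference. The mechanism is certain. The size is illustrative, because every input is assumed and an observed slope replaces the latent one.

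Three stronger readings are tempting, and the documents do not support them.

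- *Aim 2 has no covariates at all.* Extending the Aim 1 growth models plausibly brings their covariates to the growth factors.
- *Care is scored over the same months as the mediator slope, so direction cannot be established.* The posted documents do not state the scoring period. The SAP describes "change trajectories which can be used to account for differences in more distal outcomes", which suggests an intended order, and the manual supplements a protocol that is not posted. Overlap is not shown and is not part of this point.
- *The trial's main results are compromised.* The Aim 1 tests do not depend on this path.

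**What to change.** In Aim 2, state that both the mediator slope and the care outcome are regressed on arm and on the baseline depression and substance use scores used at randomisation, whether or not those scores predict attrition. Keep the growth-model framework and the bias-corrected bootstrap. Add a sentence that a significant indirect effect will be worded cautiously, because unmeasured shared causes remain.

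Do not require the full Aim 1 care list on the care path. With true mediation, no confounding and an assumed N of 150, power was as follows:

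- **First run:** 74.5% as written, 72.2% with the scores and the mediator's starting level (2.3 points lost), 64.0% with the full list (10.5 points lost).
- **Second run:** 76.8% as written, 74.0% with the scores (2.8 points lost), 60.3% with the full list (16.5 points lost).

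A further simulation, with a one-step bootstrap approximation and fewer covariates than the full list, showed no loss at N 150 (74.4% to 74.5%), so 2 to 3 points is the cautious figure. At N 300 the loss is about 1 point or less (96.5% to 96.1% in that simulation). The full list also did little about the confounding at issue.

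The remaining cost is a few sentences of SAP text. No new data are needed.
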